14.2.2 Analysis for Patients on Placebo in Initial Study

Table 14.2.2.1	BAD total score at each follow-up visit for patients on placebo in initial study – ITT population
Table 14.2.2.1a	BAD total score at each follow-up visit for patients on placebo in initial study – PP population
Table 14.2.2.2	Change in BAD total score from baseline at each follow-up visit for patients on placebo in initial study – ITT population
Table 14.2.2.2a	Change in BAD total score from baseline at each follow-up visit for patients on placebo in initial study – PP population
Table 14.2.2.3	BAD score per body region at each follow-up visit for patients on placebo in initial study – ITT population
Table 14.2.2.4	Change in BAD score per body region from baseline at each follow-up visit for patients on placebo in initial study – ITT population
Table 14.2.2.5	Proportions of responders in BAD total score at each follow-up visit for patients on placebo in initial study – ITT population
Table 14.2.2.5a	Proportions of responders in BAD total score at each follow-up visit for patients on placebo in initial study – PP population
Table 14.2.2.6	PGI-I score at each follow-up visit for patients on placebo in initial study – ITT population
Table 14.2.2.6a	PGI-I score at each follow-up visit for patients on placebo in initial

	study – PP population
Table 14.2.2.7	Proportions of responders in PGI-I at each follow-up visit for patients on placebo in initial study – ITT population
Table 14.2.2.7a	Proportions of responders in PGI-I at each follow-up visit for patients on placebo in initial study – PP population
Table 14.2.2.8	Summary of DBS settings change and outcome impacting medication use for patients on placebo in initial study – ITT population
Table 14.2.2.9	Efficacy endpoints analysis with MMRM model: Least square mean (LSM) change in score from baseline to Visit 4 for patients on placebo in initial study – ITT population
14.2.3 Analysis for Patients on DFP in Initial Study and the extension study	
Table 14.2.3.1	Comparison of change in BAD total score from baseline to month 18 for patients on DFP in initial study and patients on placebo in initial study but switched to DFP in the extension study – ITT population
14.3 Safety Analyses	
14.3.1 Adverse Events	
Table 14.3.1.1	Overall summary of adverse events – safety population
Table 14.3.1.2	Summary of adverse events – safety population
Table 14.3.1.3	Summary of adverse events related to iron deficiency – safety population
Table 14.3.1.4	Summary of adverse events related to PKAN – safety population
Table 14.3.1.5	All adverse events by severity – safety population
Table 14.3.1.6	All adverse events by seriousness – safety population
Table 14.3.1.7	All adverse events by relatedness to study medication – safety population
Table 14.3.1.8	Summary of most common (>5%) adverse drug reactions – safety population

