1.3 Potential Risks and Benefits

Risks:

The safety profile of deferiprone has been extensively characterized in patients with systemic iron overload. The most serious adverse event associated with deferiprone use is agranulocytosis, defined as a confirmed absolute neutrophil count less than $0.5 \times 10^9/L$. In

pooled clinical trials, agranulocytosis has been seen in about 1.7% of patients. The mechanism of deferiprone-associated agranulocytosis is unknown. Agranulocytosis usually resolves upon discontinuation of deferiprone, but there have been post-marketing reports of it leading to death.

The most common adverse reactions reported during clinical trials have been chromaturia, nausea, vomiting, abdominal pain, alanine aminotransferase increased, arthralgia, and neutropenia (26).

Benefits:

The findings of preclinical research and case studies suggest that deferiprone has the potential to access pathologically relevant brain iron and to produce clinical benefit in patients with PKAN.

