7.2.1.8 Adverse Events of Special Interest

An important AE that has a known association with deferiprone is **neutropenia**, defined as an absolute neutrophil count (ANC) less than $1.5 \times 10^9/L$. The severity of neutropenia is categorized as follows:

Mild neutropenia:	A confirmed ANC $\geq 1.0 \times 10^9/L$ and $< 1.5 \times 10^9/L$.
Moderate neutropenia:	A confirmed ANC $\geq 0.5 \times 10^9/L$ and $< 1.0 \times 10^9/L$.
Severe neutropenia/agranulocytosis:	A confirmed ANC $< 0.5 \times 10^9/L$.

“Confirmed” means that the ANC has been found to be within the specified range on 2 consecutive measurements a maximum of 3 days apart. If both consecutive counts are below $1.5 \times 10^9/L$ but are not within the same range, a third count is required to determine the severity category. Neutropenia is considered to be resolved when ANC is $\geq 1.5 \times 10^9/L$ on 2 consecutive counts.

Management of Neutropenia

Patients will be scheduled for weekly hematology testing throughout the study, and the results will be forwarded to the investigator. If an ANC $< 1.5 \times 10^9/L$ is detected, the patient and, if possible, the primary care physician, are to be promptly notified. In addition, since both fever and infection can be associated with neutropenia, patients will be instructed to do the following:

- In the event of a temperature ≥ 38.5 °C/101.3 °F, they are to immediately discontinue treatment and contact the investigator at the 24-hour number provided. The investigator will request that CBC and differential count be obtained.
- If they develop any symptoms of infection, they are to promptly report this to the investigator at the 24-hour number provided. The investigator will then determine whether or not treatment should be interrupted.

The management of neutropenia depends on its severity, as described below.

Mild neutropenia:

- Instruct patient to interrupt deferiprone immediately.
- Repeat the ANC count daily until resolution.
- If possible, arrange for patient to be seen by a physician the same day for a physical examination, assessment of AEs, and a review of concomitant medications/therapies. If this is not possible, contact patient by phone to obtain information on AEs and medications.
- Advise patient to enter protective isolation, if possible.
- Notify the sponsor of the event by submitting the SAE form.

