9 STATISTICAL ANALYSIS

9.1 Endpoints

9.1.1 Primary Endpoints

- Adverse events (AEs): Frequency, severity, time to onset, duration, and relatedness to study product

- Serious adverse events (SAEs): Frequency, severity, time to onset, duration, and relatedness to study product
- Number of discontinuations due to AEs
- Hematology assessments
- Blood chemistry assessments
- ECG assessments

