4.4 Safety Analyses

The safety endpoints include:

- Adverse events (AEs): Frequency, severity, time to onset, duration, and relatedness to study product
- Serious adverse events (SAEs): Frequency, severity, time to onset, duration, and relatedness to study product

-
- Number of discontinuations due to AEs
 - Hematology assessments
 - Blood chemistry assessments
 - ECG assessments

All safety data collected will be presented in listings and summary tables or graphs to give an overview of the safety findings. All safety endpoints will be analyzed based on the safety population. For patients continuing on deferiprone in the extension study, this time period will be from the start of TIRCON2012V1 to the completion of TIRCON2012V1-EXT; for those who received placebo in the initial study and are switching to deferiprone in the extension study, it will be from the start to the completion of the extension study.

For those patients who do not follow the scheduled time window exactly for each visit or withdraw from the study early, the following time window will be employed to classify the safety data into each scheduled visit according to the time elapsed from the first medication date (date of exposure) to the assessment date:

Month 1.5 visit: 0.75 to <2.25 months

Month 3 visit: 2.25 to <4.5 months

Month 6 visit: 4.5 to <9 months

Month 12 visit: 9 to <15 months

Month 18 visit: 15 to <21 months

Month 24 visit: 21 to <27 months

Month 30 visit: 27 to <33 months

Month 36 visit: 33 to <39 months

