4.4.1 Adverse Events

A summary table of adverse events will include the following information:

- number of patients exposed to study treatment,
- number of patients experiencing at least one AE,
- number of patients experiencing at least one severe AE,

- number of patients experiencing at least one serious AE,
- number of patients experiencing at least one drug-related AE,
- number of deaths,
- total number of patients withdrawn,
- number of withdrawals due to AEs.

All adverse experiences will be coded using MedDRA (Medical Dictionary for Regulatory Activities) and will be summarized by MedDRA System Organ Class (SOC) and Preferred Term. Adverse events will be defined as: 1) AEs that occurred or worsened (increased in intensity and/or frequency) on or after the first dose of study medication, 2) AEs with a missing start date or a stop date on or after the first dose of study medication, 3) AEs with both a missing start and stop date. Events that occur within 14 days after treatment discontinuation will also be considered AEs. Serious adverse events that occur within 30 days after treatment discontinuation will be included in the database.

Adverse events will be summarized using the total number of AEs, the total number and percent of patients who experience an AE, and the number and percent of patients who experienced an AE within each SOC (and preferred term within an SOC). The rate of each AE (per 100 patient years) will also be calculated. AEs will also be presented by intensity (mild, moderate, severe), by seriousness (serious, non-serious), and by relationship to study medication (at least possibly related, not related). The number and percentage of patients who are withdrawn from the study due to AEs will be calculated, and the AEs involved will be summarized in a frequency table. Time to onset and duration of all AEs with an incidence of >5%, and of any AEs of special interest (e.g., worsening of dystonia), will be summarized with descriptive statistics.

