Cccccc	x (x.x)	x (x.xx)	x (x.x)	x (x.xx)
Cccccc	x (x.x)	x (x.xx)	x (x.x)	x (x.xx)
Cccccc	x (x.x)	x (x.xx)	x (x.x)	x (x.xx)
.....	x (x.x)	x (x.xx)	x (x.x)	x (x.xx)

Table 14.3.1.8 Summary of most common (>5%) adverse drug reactions – safety population

	DFP			
	Exposure (subject-years): x.xx			
	Total Subjects Exposed: xx			
	Total Events: xxx			
	Total Subjects Reporting: xx			
System Organ Class Preferred Term	N Subjects (%)	N Events (Rate/100 patient years)	Time to onset (Days) Mean (SD) Median (Min, Max)	Duration (Days) Mean (SD) Median (Min, Max)
CCCCC	x (x.x)	x (x.xx)	xx.xx (xx.x) xx.x (xx.x, xx.x)	xx.xx (xx.x) xx.x (xx.x, xx.x)
Ccccc	x (x.x)	x (x.xx)	xx.xx (xx.x) xx.x (xx.x, xx.x)	xx.xx (xx.x) xx.x (xx.x, xx.x)
.....	x (x.x)	x (x.xx)	xx.xx (xx.x) xx.x (xx.x, xx.x)	xx.xx (xx.x) xx.x (xx.x, xx.x)

Table 14.3.2.1.1 Hematology at each visit – safety population

Test	Visit	DFP (N=xx)
Hemoglobin (g/L) n Mean (SD) Median (Min, Max)	Baseline	xx xx.xx (xx.x) xx.x (xx.x, xx.x)
	Month 1.5	xx xx.xx (xx.x) xx.x (xx.x, xx.x)
	Month 3	xx xx.xx (xx.x) xx.x (xx.x, xx.x)
	Month 6	xx xx.xx (xx.x) xx.x (xx.x, xx.x)
	Month 12	xx xx.xx (xx.x) xx.x (xx.x, xx.x)
	Month 18	xx xx.xx (xx.x) xx.x (xx.x, xx.x)
	Month 24	xx xx.xx (xx.x) xx.x (xx.x, xx.x)

	Month 30	XX XX.XX (XX.X) XX.X (XX.X, XX.X)
	Month 36	XX XX.XX (XX.X) XX.X (XX.X, XX.X)
Repeat for other hematology parameters

Table 14.3.2.1.2 Hematology analysis: change in value at the end of study (Visit 4) – safety population

	Visit	n Mean (SD)	Change from Baseline n Mean (SD)	p-value [§]
Hemoglobin (g/L)	Baseline	xx xx.xx (xx.x)		
	Visit 4	xx xx.xx (xx.x)	xx xx.xx (xx.x)	0.xxxx
Repeat for other hematology parameters

§ p-value from paired t-test

Table 14.3.2.1.3 Shift table comparing three laboratory value categories at baseline and end of study: Hematology – safety population

Laboratory Test	Treatment	Baseline	End of study			Total
			Low	Normal	High	
Hemoglobin	DFP	Low	xx	xx	xx	xx
		Normal	xx	xx	xx	xx
		High	xx	xx	xx	xx
		Total	xx	xx	xx	xx
Repeat for other tests of interest						

Table 14.3.2.2.1 Blood biochemistry at each visit – safety population

Test	Visit	DFP (N=xx)
Seum Ferritin (ug/L) n Mean (SD) Median (Min, Max)	Baseline	xx xx.xx (xx.x) xx.x (xx.x, xx.x)
	Month 1.5	xx xx.xx (xx.x) xx.x (xx.x, xx.x)
	Month 3	xx xx.xx (xx.x) xx.x (xx.x, xx.x)
	Month 6	xx xx.xx (xx.x) xx.x (xx.x, xx.x)
	Month 12	xx xx.xx (xx.x) xx.x (xx.x, xx.x)
	Month 18	xx xx.xx (xx.x) xx.x (xx.x, xx.x)

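### The only planned table of adverse-event time to onset and duration is limited to adverse drug reactions above 5%, which is narrower than the scope the SAP and protocol text commit to

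*SAP*

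**What the plan says.** **Endpoints.** Protocol 9.1.1 lists as a primary endpoint "Adverse events (AEs): Frequency, severity, time to onset, duration, and relatedness to study product". It has a matching item for SAEs, which SAP 4.4 repeats: "Serious adverse events (SAEs): Frequency, severity, time to onset, duration, and relatedness to study product".

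**Analysis text.** SAP 4.4.1 commits to descriptive statistics for "Time to onset and duration of all AEs with an incidence of >5%, and of any AEs of special interest (e.g., worsening of dystonia"), and protocol 9.4.1.4 has the same scope. Neither sets a relatedness condition for common AEs, and neither sets a minimum incidence for events of special interest.

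**Events of special interest.** Protocol 7.2.1.8, which carries that title, is about neutropenia in three severity categories. It opens: "An important AE that has a known association with deferiprone is" neutropenia. The analysis text gives worsening of dystonia as its example.

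**Planned output.** SAP section 5 presents its list as the tables and figures to be produced. Among the eight AE tables, the one with timing columns is Table 14.3.1.8, "Summary of most common (>5%) adverse drug reactions – safety population". Its shell in SAP section 7 has the columns "Time to onset (Days) Mean (SD) Median (Min, Max") and "Duration (Days) Mean (SD) Median (Min, Max").

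**The concern.** The text and the table list set different scopes for the same primary endpoint. A programmer working from the list and shells would produce timing statistics only for events that pass two filters, relatedness and frequency, neither of which the text imposes in that form.

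Each filter matters here. The study is open-label and every patient takes deferiprone, so the relatedness filter depends on the investigator's judgement with no concurrent control. The frequency filter works against uncommon events, and SAP 4.4.1 exempts events of special interest from it. In a study whose primary objective is long-term safety, when such events start and how long they last is a central question. If the scope stays unsettled until the data are seen, the choice of which timings to tabulate can depend on the results.

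**Working it through.** **Step 1. Compare the commitment with the listed tables (SAP sections 5 and 7).**

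| Table | Events covered | Onset and duration? |
|---|---|---|
| 14.3.1.1 | Overall AE summary | No, counts and percentages of patients |
| 14.3.1.2 | All AEs | No, patients, events, rates |
| 14.3.1.3 | Related to iron deficiency | No, same layout |
| 14.3.1.4 | Related to PKAN | No, same layout |
| 14.3.1.5 | By severity | No, same layout |
| 14.3.1.6 | By seriousness | No, same layout |
| 14.3.1.7 | By relatedness | No, same layout |
| 14.3.1.8 | Adverse drug reactions above 5% | Yes |

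No table is listed for events of special interest. The SAP expands ADR in its abbreviations but does not define it. I take it to mean an AE at least possibly related to study drug, following the relatedness split in SAP 4.4.1. The SAP also does not say whether the 5% refers to the incidence of the AE or of the ADR.

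Set against the commitment, Table 14.3.1.8 leaves out:

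1. AEs above 5% judged unrelated.
2. Events of special interest at or below 5%.
3. Events of special interest judged unrelated, at any incidence.

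An event of special interest that is also a drug reaction above 5% would appear, but not as a separate group.

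**Step 2. What above 5% means in patients.** SAP 3.2 gives 44 + 24 = 68 enrolled. Assume all are dosed. Then 3/68 = 4.4% and 4/68 = 5.9%, so an event needs at least 4 patients.

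**Step 3. Chance that an event occurs but misses the table because of the 5% cut-off.** The plan has no figure of its own to reproduce; SAP 3.2 states that no formal sample size calculation was made. Let X be the number of patients with the event, X ~ Binomial(68, p), with every occurrence judged related so that only the frequency filter acts. Then

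P(1 to 3 patients) = P(X ≥ 1) − P(X ≥ 4), where P(X ≥ 1) = 1 − (1 − p)^68.

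| Assumed p | Expected patients, 68p | P(X ≥ 1) | P(X ≥ 4) | P(1 to 3) |
|---|---|---|---|---|
| 1% | 0.68 | 0.495 | 0.005 | 0.490 |
| 1.7% | 1.16 | 0.688 | 0.029 | 0.660 |
| 3% | 2.04 | 0.874 | 0.147 | 0.727 |
| 5% | 3.40 | 0.969 | 0.444 | 0.526 |
| 8% | 5.44 | 0.997 | 0.803 | 0.193 |

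The last column is taken from unrounded values. The 1.7% comes from protocol 1.3 ("agranulocytosis has been seen in about 1.7% of patients", from pooled clinical trials); the other rates are assumptions to show the range. For an event judged unrelated no calculation is needed: it is left out whatever its count.

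**The case against.** The strongest reply is that SAP 4.4.1 is the governing text and already has the right scope. Section 5 allows for tables to be added, and section 7 says the shells show a general layout that may change. On this view the fault is a mismatch between text and output list, not a decision to drop an analysis. That description is fair. But room to add tables is not a commitment to add these, and the filters are in the listed title of Table 14.3.1.8, not only in its layout.

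Second, uncommon events are visible elsewhere. SAEs, withdrawals due to AEs and deaths have listings and narratives (SAP 4.4.1). Section 6 plans listings of AEs, drug reactions, SAEs and serious drug reactions, and ANC plots by patient. Protocol 7.2.1.8 has every neutropenia category notified on the SAE form. For one to three cases, a narrative with an ANC plot may tell more than a mean and SD. This stands and limits the harm, but these outputs are not the promised descriptive statistics.

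Third, 1.7% may not apply here. Protocol 1.3 describes a safety profile established in systemic iron overload, and protocol 1.1.2 gives 75 to 99 mg/kg/day for transfusional iron overload, against up to 30 mg/kg/day in this study. All 68 patients completed the initial study, and 44 of them did so on deferiprone. Agranulocytosis is also only the most severe category; protocol 1.3 counts neutropenia among the common reactions, so neutropenia overall might pass 5%. This stands, so the figure is used only as one point in a range.

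Some stronger readings are tempting but not supported:

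- *A primary endpoint would go unreported.* The text commits to the summary, and individual events are listed.
- *Agranulocytosis timing would be missing with about 97% probability.* That is 1 − 0.029 and includes the 31% chance of no case, when nothing is omitted. The relevant figure is 66%. At 3% incidence, 85% likewise becomes 73%.
- *Worsening of dystonia will drop out because it will be attributed to PKAN.* Protocol 7.2.1.3 lets an event be possibly related even when concurrent disease could explain it, and possibly related falls in the related group. Exclusion can happen, but the documents do not show it to be likely.
- *The SAP contradicts the protocol on neutropenia.* Dystonia is given only as an example, in the protocol's analysis text too. Naming neutropenia would be a clarification.
- *A separate SAE timing summary is promised.* SAE onset and duration are listed as endpoints, but neither analysis text promises a separate summary of them.

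**Conclusion.** The point holds as an internal inconsistency that should be corrected. The one table that reports time to onset and duration has a narrower scope than SAP 4.4.1 and protocol 9.4.1.4, for a measure that is a primary endpoint. What is lost is the summary statistics for common AEs judged unrelated, and for events of special interest that are uncommon or judged unrelated. The events themselves are not lost from the report.

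For the 5% cut-off alone, the chance that an event is seen but not tabulated is 0.49 to 0.73 over assumed incidences of 1% to 5%, falling to 0.19 at 8%. This assumes 68 dosed patients, one common incidence, independence between patients and every occurrence judged related. It ignores the difference in exposure between the 44 patients followed on deferiprone from the start of the initial study and the 24 followed from the switch. The mismatch itself depends on none of these figures. It needs only the reading of ADR as an AE at least possibly related to study drug.

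**What to change.** 1. Widen Table 14.3.1.8 to all AEs above 5% regardless of relatedness, and show drug reactions as a subset.
2. Add rows at any incidence for events of special interest: neutropenia by the protocol 7.2.1.8 categories, and worsening of dystonia. Naming both in SAP 4.4.1 would remove doubt.
3. Define ADR in the SAP, and state whether the 5% is the incidence of the AE or of the ADR.
4. Optionally, add an SAE subset to the same table. SAP 4.4.1 does not promise it, but SAE onset and duration are listed as primary endpoints.

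The cost is one re-specified table and a few lines of text. It uses AE dates and neutrophil counts that the protocol already collects (hematology weekly, and ANC daily during neutropenia until resolution), so no new data are needed. The change should be fixed before the data are analysed.

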14.3.2 Hematology and Biochemistry and Urinalysis	
Table 14.3.2.1.1	Hematology at each follow-up visit – safety population
Table 14.3.2.1.2	Hematology analysis: change in value at the end of study (Visit 4) – safety population
Table 14.3.2.1.3	Shift table comparing three laboratory value categories at baseline and end of study: Hematology – safety population
Table 14.3.2.2.1	Blood biochemistry at each follow-up visit – safety population
Table 14.3.2.2.2	Blood biochemistry analysis: change in value at the end of study (Visit 4) – safety population
Table 14.3.2.2.3	Shift table comparing three laboratory value categories at baseline and end of study: Blood biochemistry – safety population

Table 14.3.2.3.1 Proportions of abnormal urinalysis results in each visit – safety population

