4.5 Patient Withdrawal

Patients have the right to withdraw from the study at any time and for any reason without consequence to future care by the investigator or study center.

A patient may be withdrawn from the study at any time, at the discretion of the investigator, for any of the following reasons:

- Medical or safety reasons considered significant by the patient and/or the investigator
- Requirement for concomitant medication that might interfere with the evaluation of study treatment or may be contraindicated
- Occurrence of other illnesses that might affect the patient's further participation in the study or evaluation of study treatment
- A protocol deviation that might interfere with study assessments, as judged by the investigator
- Repetitive patient non-compliance with the protocol or with instructions of the investigator
- Participation in another clinical trial at any time during the conduct of this study
- Any other situation where, in the opinion of the investigator, continuation of the study would not be in the best interest of the patient

A patient **must** be withdrawn from the study if any of the following conditions apply:

- Pregnant or planning to become pregnant (see [Section 7.2.4](#), Procedures in Case of Pregnancy)

- Occurrence of any adverse event characterized as life-threatening or disabling that is not associated with the patient's primary diagnosis and that is assessed as at least possibly related to study drug by the investigator or the sponsor
- Non-compliance with weekly hematology blood counts (3 or more consecutively missed visits will result in automatic withdrawal)
- Termination of the study by the sponsor
- Occurrence of moderate neutropenia or severe neutropenia/agranulocytosis (see [Section 7.2.1.8](#), Adverse Events of Special Interest)

Patients who decide to withdraw participation in the study should always be contacted, if possible, in order to ask about the reason for withdrawal, whether any adverse events (AEs) occurred, and use of concomitant medications. A withdrawn patient should return for an Early Termination Visit. All investigational product and materials should be returned. If any AEs occurred, the investigator must attempt to follow up the outcome for 30 days post-termination.

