7.2.2 Laboratory Measurements

Samples for laboratory safety assessments will be taken at the time points indicated below. If a patient withdraws from the study, the End of Study procedures are to be performed at an early termination visit.

Hematology: Complete blood count (CBC), including total WBC, ANC, platelet count, and hemoglobin	Weekly
Blood chemistry: Serum ferritin, total protein, GGT, LDH, sodium, potassium, chloride, glucose, total, bilirubin, AST, ALT, albumin, blood urea nitrogen, calcium, creatinine, uric acid, alkaline phosphatase, and amylase	Visits 1, 2, 3, and 4
Urinalysis: pH, specific gravity, glucose, protein, ketones, and blood. If indicated by the dipstick, sediment microscopy will be performed.	Visits 1, 2, 3, and 4
Pregnancy testing: Serum pregnancy tests will be performed for all sexually active females of childbearing potential (unless the investigator determines there is no reasonable risk of pregnancy because of significant incapacity)	Visits 1, 2, 3, and 4

The investigator must review and interpret each laboratory report, and document the review by signing or initialing and dating the report. Any laboratory values that fall outside a clinically accepted range, or values that differ significantly from previous values, must be marked by the investigator as either “CS” (clinically significant) or “NCS” (not clinically significant). Any that are marked as CS must be further explained and documented as an AE.

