3.5 Missing Data Handling and Derivation Rules

For safety data analysis, no imputation will be performed on the missing data and analysis will be based on observed cases.

For efficacy endpoints, the continuous variables will be summarized and analyzed as recorded on the case report forms (CRFs). If statistically significant imbalances are detected in the incidence of changes in DBS settings and outcome impacting medication use as well as the frequency of PRN drug or rescue medication between the initial study and the extension study, a Mixed-Effect Model Repeated Measure (MMRM) model will be used as the analysis method to compare the change in score from baseline between the initial study and the extension study for patients who received placebo in initial study (TIRCON2012V1) and the analysis will be based on observed cases. If no significant imbalance was detected, the paired t-test will be used as the analysis method and the last observed data will be used.

For the efficacy analysis on all patients who received DFP during the initial and the extension study, the last observation will be used to calculate the change from baseline for patients terminated early. As a sensitivity analysis, for early termination due to worsening of disease conditions or inadequate efficacy of the drug, as indicated in the CRF, the “worst score” method will be used for data imputation. That is, for continuous variables such as BAD total score at a particular time point, the worst score of all patients will be used to impute the missing data at that time point. For categorical variable such as responder, the worst category (treatment failure) will be assigned. For missing data due to missed visit, the last observation will be used to fill the void.

For BAD total score, if one or several component scores cannot be measured, then the same component score from the last visit will be carried forward and if it is also missing, the score from the next visit will be carried backward to fill the missing component score(s) before the total score is calculated.

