4.4.2 Laboratory Data

Descriptive statistics for each clinical laboratory test will be presented for each visit as defined above for hematology and for blood biochemistry. For each test, if multiple measurements are taken on the same scheduled visit for a subject, average value will be used for this subject at that visit. According to the laboratory normal ranges, laboratory test results will be categorized as low (< lower normal limit), normal (within normal range), and high (> upper normal limit). Shift tables comparing the distributions of these three categories at baseline versus end of study for parameters of interest will be presented.

Continuous data will also be presented graphically for examination of possible trends.

Clinically significant laboratory values will be reported in the adverse event analysis.

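### The end-of-study laboratory change tests use Visit 4 observed cases, so patients withdrawn early, including those withdrawn for neutropenia, are not in them; the shift tables leave *end of study* undefined

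*SAP*

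**What the plan says.** Hematology and blood chemistry are primary endpoints (Protocol 9.1.1). The SAP plans two kinds of end-of-study summary for them.

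- **Change tables** (14.3.2.1.2 hematology, 14.3.2.2.2 chemistry). The first is titled "Hematology analysis: change in value at the end of study (Visit 4", and the second uses the same wording. The shells have a Visit 4 row and a paired t-test.
- **Shift tables** (14.3.2.1.3 and 14.3.2.2.3). The first is titled "Shift table comparing three laboratory value categories at baseline and end of study: Hematology". SAP 4.4.2 says "Shift tables comparing the distributions of these three categories at baseline versus end of study for parameters of interest will be presented". Neither place mentions Visit 4, and no test is attached.

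Two general rules decide who has a Visit 4 value. SAP 3.5 states: "For safety data analysis, no imputation will be performed on the missing data and analysis will be based on observed cases". SAP 4.4 says that for patients who "withdraw from the study early, the following time window will be employed to classify the safety data into each scheduled visit", the placement goes by time since the first deferiprone dose.

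Protocol 4.5 lists among the mandatory reasons for withdrawal "Occurrence of moderate neutropenia or severe neutropenia/agranulocytosis". Protocol 7.2.2 adds: "If a patient withdraws from the study, the End of Study procedures are to be performed at an early termination visit".

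**The concern.** A patient taken off study for a low neutrophil count is one whose result most needs to be in an end-of-study summary of neutrophils. If the summary is restricted to samples in the final visit window, that patient is absent because of the very variable being summarised. The remaining patients are selected for having tolerated the drug, and the mean change in ANC will tend to look milder than it was in everyone treated. In the shift table the loss would be more visible, since the missing patient belongs in the Low column.

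The data to avoid this are collected: weekly counts throughout, and a further sample at early termination. For the all-patient efficacy analysis, SAP 3.5 does use the last observation of patients who stop early. It gives no such rule for safety.

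**Working it through.** The plan states no figure on this point, so there is none to reproduce. The check traces the rules and then gives an illustrative size.

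**1. Who has a Visit 4 laboratory value**

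- Patients switched from placebo: Visit 4 is month 18 on deferiprone. SAP 4.4 gives "Month 18 visit: 15 to <21 months".
- Patients continuing on deferiprone: Visit 4 is month 36, with a window of 33 to under 39 months.
- A sample drawn earlier is filed under an earlier visit. With observed cases only, nothing carries it forward.
- Taking the extension to start at month 0 (switchers) or month 18 (continuers), the uncovered part is 15 of 18 months in both groups: 15/18 = 83%. A withdrawal whose last sample falls inside the final window still counts.

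**2. Whether the exclusion depends on the result**

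- ANC: yes. Protocol 7.2.1.8 defines moderate neutropenia as a confirmed count of at least 0.5 and below 1.0 × 10⁹/L, and severe as below 0.5. Either forces withdrawal.
- Chemistry: not directly. Protocol 4.5 lists no chemistry value as a mandatory reason. A chemistry result can lead to withdrawal only through the adverse-event criteria or the investigator's discretion.

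**3. How likely a relevant case is**

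Inputs: 68 patients enrolled, 44 continuing + 24 switched (SAP 3.2); agranulocytosis in about 1.7% of patients in pooled trials (Protocol 1.3). Applying that rate here is an assumption.

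- Newly exposed patients: expected 24 × 0.017 = 0.41; P(at least one) = 1 − 0.983²⁴ = 0.34.
- All 68: expected 68 × 0.017 = 1.16; P(at least one) = 1 − 0.983⁶⁸ = 0.69. This treats the 44 continuers as newly at risk, although they had already completed 18 months on the drug, so the first figure is the fairer one.
- Moderate neutropenia would add cases, but the documents give no rate for it.

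**4. Effect on the mean ANC change**

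Let k patients be excluded, and let d be their mean change minus that of the others. Restoring them moves the mean over 68 patients by (k/68) × d. This takes all the other patients to have a Visit 4 value. Assume d between −2.0 and −3.5 × 10⁹/L, and a standard deviation of change between 1.0 and 2.0, so that the standard error is SD/√68.

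| k | Shift in mean (× 10⁹/L) | Size in standard errors |
|---|---|---|
| 1 | −0.03 to −0.05 | 0.12 to 0.42 |
| 2 | −0.06 to −0.10 | 0.24 to 0.85 |
| 4 | −0.12 to −0.21 | 0.49 to 1.70 |

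In the shift table the same k patients would add up to k to the Low column, if their last values lie below the lower normal limit.

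**5. Why the value used must not be a window average**

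SAP 4.4.2 averages multiple measurements at one visit. If the 26 weekly counts of a six-month window were averaged, an assumed usual ANC of 4.0 with a single count of 0.4 would give (25 × 4.0 + 0.4)/26 = 3.86, and the low count would disappear.

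**The case against.** The strongest reply is that an early-termination sample may already count as Visit 4. The protocol's schedule puts Visit 4 and early termination in one column, Protocol 5.1 describes them under one heading, and Protocol 7.2.2 has the end-of-study samples taken at early termination. Using a sample that was actually drawn is not imputation, so SAP 3.5 would not forbid it.

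This stands for the shift tables. They never say Visit 4, so the fault there is an undefined term, not a stated exclusion. It does not stand for the change tables. SAP 4.4 deals expressly with early withdrawers and places their samples by elapsed time, and the last-observation rule in SAP 3.5 is limited to efficacy.

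A second reply is that the events are reported elsewhere, and this stands. Neutropenia of any grade goes to the sponsor on the serious adverse event form. Clinically significant values enter the adverse event analysis. Withdrawals and serious events are listed with narratives, and there are by-visit hematology tables, listings and an ANC plot for each patient. A mean change at one late visit is also not where a rare neutropenia would be detected.

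A third reply is that a last-value rule can miss the lowest count, because dosing is interrupted at mild neutropenia and daily counts follow. This limits the remedy without defeating it: the count that triggers stopping is itself drawn on treatment.

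**Conclusion.** The exclusion is real in Tables 14.3.2.1.2 and 14.3.2.2.2, and for ANC it depends on the outcome. For chemistry it is an ordinary loss of early withdrawers. For Tables 14.3.2.1.3 and 14.3.2.2.3 the defect is a missing definition: if *end of study* is read as Visit 4, a patient withdrawn for neutropenia before the final window would be missing from the Low cell.

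A reader might infer that the whole primary laboratory analysis is restricted to completers and conceals toxicity. The documents do not support that. Patients who withdraw within the final window are included, the shift tables are not tied to Visit 4, no chemistry value forces withdrawal, and the events appear in several other planned outputs. The defect is limited to the end-of-study summaries.

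Its size is illustrative. The 34% chance of at least one agranulocytosis case among 24 new starters assumes that the 1.7% from other trials applies here. The shifts in the mean rest on assumed ANC changes and are small for one or two patients. The documents do not show how many patients withdrew for neutropenia.

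**What to change.** In SAP 4.4.2, define laboratory *end of study* for all four tables as each patient's single last on-treatment value (for hematology, the last weekly count drawn on treatment). If there is none, use the early-termination sample. State that this is one value and not the window average. Show the number of early terminators included in each table, and keep the Visit 4 observed-case result as a supplementary row.

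The cost is a few lines of SAP text and one derivation on data already collected. There are two downsides. Values will come from different lengths of exposure, which the retained Visit 4 row lets the reader judge. The last on-treatment value may also precede the lowest count, so the tables will still not show the nadir in every case.
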